### **Intra-Operative**

1. Dural injury during craniotomy/craniectomy that cannot be eliminated by widening the craniotomy/craniectomy to recreate the native dural cuff.
2. Patient has a gap between durotomy edges of greater than 2mm after primary dural closure.
3. Approaches that would not allow sutured dural closure such as trans-sphenoidal or trans-labyrinthine-/petrosal/-mastoid. Superficial penetration of mastoid air cells is allowed.
4. Use of implants made of synthetic materials coming into direct contact with dura (e.g., PTFE patches, shunts, ventricular and subdural drains, existing CSF drains.)
5. Use of other fibrin sealants or PEG-based sealants on the dural closure. Approved fibrin sealants may be used for hemostasis if not in contact with the dura.
6. Hydrocephalus, except occlusive hydrocephalus caused by posterior fossa pathology or incompletely open cerebrospinal fluid pathways to be treated during the planned surgical procedure.
7. Placement of Gliadel Wafers
8. Intersecting durotomy scars in the surgical path from a previous operation that cannot be completely removed by the planned dural resection.
9. Two or more separate cranial dural defects, including defects from ventricular cannulation and ventriculo-peritoneal shunting
10. Subjects with any other intra-operative findings identified by the surgeon that may preclude the conduct of the study procedure.
11. Confined bony structures where nerves are present where neural compression may result due to swelling.

## **5. Randomization**

### **5.1 Overview**

Randomization will be used to avoid bias in the assignment of treatment to each subject, to increase the likelihood that attributes of the subject are evenly balanced across treatment groups, and to enhance the validity of statistical comparisons across treatment groups.

## 6. Investigational Product and Comparators

### 6.1 EVICEL® Fibrin Sealant

#### 6.1.1 Formulation

EVICEL® is a human plasma-derived fibrin sealant. EVICEL® consists of two components: a concentrate of Human Fibrinogen (referred to as Biological Component 2; BAC2) and a solution of Human Thrombin, which incorporates calcium. No material of animal origin is present in the product. A purpose- designed application device is used to apply EVICEL® to the surgical site by spraying or dripping. The applicator device has been designed to ensure even mixing of the two components.

#### Composition of EVICEL®

	Human Fibrinogen	Human Thrombin
Active Ingredient	Concentrate of human fibrinogen (55-85 mg/mL)*	Human thrombin (800-1200 IU/mL)
Other ingredients	Arginine hydrochloride, Glycine, Sodium chloride, Sodium citrate, Calcium	Calcium chloride, Human albumin, mannitol, Sodium acetate, Water for injection (WFI).

	chloride, Water for injection (WFI)	
--	-------------------------------------	--

\*In EU, specified as 50-90 mg/mL human clottable protein containing mainly fibrinogen and fibronectin.. Each mL of Evicel® contains 11.6-12.9 mg sodium.

### 6.1.2 Labeling and Packaging

The investigational product will have two vials contained within a single box. The product will be labeled according to local regulatory requirements and may contain the following information:

- Name, address and telephone number of Sponsor
- Protocol number
- EudraCT number
- Vial contents (volume of solution and concentration of active ingredients)
- Storage conditions
- Reference to the Package Leaflet for instructions of preparation and use in the Investigator’s Brochure
- “For Clinical Trial Use Only”
- “Caution: New Drug—Limited by Federal Law to Investigational Use”
- Lot number
- Expiry date

### 6.1.3 Application Device

The application device is commercially available in the US, EU and multiple other countries. It will be used according to its intended instructions and is not considered an investigational product in regions where available. The applicator will be labeled according to local regulatory requirements, and may contain the following information:

- Name, address and telephone number of Ethicon, Inc.
- Protocol number
- “For Clinical Trial Use Only”

### 6.1.4 Accessory Tips

Certain accessory tips are commercially available in several countries. They will be used according to their intended instructions and are not considered as an investigational product in regions where available.

There will be three accessory tips provided for use with the application device:

- Standard yellow tip (provided with application device)
- 4cm tip (control tip)
- Airless Spray Tip

Accessory tips may be used according to surgeon preference. Tips will be used in accordance with their Product Assembly Guide. Depending on its regulatory status and local regulatory requirements, the product will be labeled according to local regulatory requirements, and may contain the following information:

- Name, address and telephone number of Ethicon, Inc.
- Protocol number
- “For Clinical Trial Use Only”

### **6.1.5 Pressure Regulators**

Pressure regulators may be supplied by request. The pressure regulators are commercially available. They will be used according to their intended instructions and are not considered an investigational product.

### **6.1.6 Shipping, Handling, and Storage Conditions**

Distribution of EVICEL® to the clinical sites will be performed by a qualified distribution center with proper inventory and quality control capabilities once all the necessary documentation and approvals are obtained. For distribution in the EU, a qualified person (QP) release will be done prior to distribution.

The two components of the EVICEL® Kit are frozen, and must be stored at –18°C or colder. EVICEL® will be shipped to each site on dry ice during which the temperature will be monitored continuously. Once at the site, the product will be stored in a freezer at –18°C or colder, according to the product label.

The application devices, tips, and pressure regulators will be shipped and stored at ambient temperature.

### **6.1.7 Preparation**

The two frozen components of EVICEL® (BAC2 and Thrombin) must be thawed before use, using one of the following methods:

- 2-8°C (refrigerator): vials thaw within one day; or
- 20-25°C (room temperature): vials thaw within one hour; or
- 37°C; vials thaw within ten minutes and should not be left at 37°C for more than 10 minutes. The temperature must not exceed 37°C.

Thawed, unopened vials can be stored at 2-8°C for up to 30 days. Thawed vials must not be re-frozen, and product taken out of the refrigerator should not be returned to the refrigerator.

After thawing, preparation of the product must occur in a sterile surgical field. The two components should be drawn into the application device, following directions enclosed in the application device package. Both syringes must be filled with equal volumes, and should not contain air bubbles. Selection of the appropriate application/accessory tip will be left to the discretion of the surgeon.

### **6.1.8 Dose, Route, and Duration of Administration**

For each subject, at least one kit of EVICEL® will be thawed and available for administration prior to randomization. EVICEL® will be applied to cover the entire length of the suture line and the adjacent area of the dura to produce a thin, even layer (approx. 1mm thickness). If necessary, a second layer of EVICEL® may be applied. A cure time of 1-2 minutes should be allotted between applications to allow for the clot formation and stabilization. The amount of EVICEL® required depends upon the area of tissue to be treated and the method of application.

Application can be made by dripping or spraying in accordance with the EVICEL® Investigator Brochure, Accessory Tip Directions and Device and Pressure Regulator IFU.

## **6.2 DuraSeal® Dural Sealant System**

DuraSeal® will be stored, handled, prepared, and applied according to its label and instructions for use (IFU) or package insert. If necessary, a second layer of DuraSeal™ may be applied.

### **6.3 Investigational Product Dispensation and Accountability**

A dispensing/accountability log will be kept by the designated study personnel containing information on the date of administration, subject ID #, quantity of EVICEL® and DuraSeal™ (if applicable) dispensed, details of remaining product, and subsequent destruction (if applicable). The study monitor will verify these logs during the course of the study. The study product will be stored according to the IB or IFU, respectively, and be kept in a secured area with access restricted. Study product is to be used for study subjects only.

### **6.4 Concomitant Medications**

#### **6.4.1 Documentation of Concomitant Medications**

Indication and start-stop dates of concomitant medications administered from 24 hours prior to surgery up to the 60-day follow-up visit will be recorded. This will include medications that subjects are using chronically.

Anesthetics used for the study surgery and over the counter (OTC) drugs will not be recorded as concomitant medication (with the exception of prophylactic aspirin and those administered to treat adverse events, which should be documented). Concomitant medications used to treat Adverse Events must also be documented, including OTC medications. Doses and routes of administration are not required to be reported.

## **7. Study Evaluations**

### **7.1 Study Procedures**

The schedule of events included in the synopsis summarizes the frequency and timing of the study procedures. All assessments will be performed by the investigator or other study personnel with delegation of authority. Data collected for the subject during the study will be recorded in the subject's medical records, and study worksheets/source documents, as appropriate, and transcribed into the eCRF.

#### **7.1.1 Screening**

Prospective patients will be screened within 30 days prior to surgery. All prospective patients should be listed in the screening and enrollment log. Patients screened but not consented or enrolled should be recorded with a reason for not enrolling. Prior to any study specific procedures, subjects will be appropriately consented and the consenting process documented. Subjects (or legally authorized representative) will be asked to sign an Informed Consent Form. Once the Informed Consent Form is signed, study related information, including information obtained as part of standard clinical practice, may be collected as part of the protocol.

The following tests and activities will be performed or collected at the screening visit. The timing of these activities may occur based on routine hospital practice and may be done up to the day of, but prior to, the study surgery:

- Informed consent process
- Allocation of screening number
- Assessment of pre-operative inclusion and exclusion criteria for subject eligibility
- Documentation of demography (e.g. age, ethnic origin)

- Physical examination, including documentation of relevant medical and surgical history
- Documentation of smoking status, alcohol consumption, history (family and personal) of thromboembolic events

### 7.1.2 Baseline

The following activities/assessments will be done within 24 hours prior to the procedure. The timing of these activities may occur based on routine hospital practice and may overlap with some of the Screening (see Section 7.1.1) activities.

- Review of pre-operative inclusion and exclusion criteria to confirm subject pre-operative eligibility. If the subject is no longer eligible, the reason for screen failure will be documented in the source documentation and the screening log
- Documentation of concomitant medications as outlined in Section 6.4
- Documentation of any changes in medical history since the screening visit (if done on a separate visit from Baseline).
- Laboratory evaluations – samples can be drawn within 7-days prior to the procedure. Labs taken closest to procedure should be used.
  - Electrolyte, blood urea nitrogen (BUN), creatinine
  - Complete blood count (CBC) with differential
  - Liver function tests
  - Serum or urine pregnancy test (if applicable)

### 7.1.3 Surgical Procedure

The investigator will use his or her standard surgical techniques for the surgical procedure. Use of a tissue based patch is permitted for primary sutured dural closure if a watertight seal can be achieved. Upon completion of the sutured dural repair, the closure will be evaluated for intraoperative CSF leakage with a baseline Valsalva maneuver performed to an intra-thoracic pressure between 20-25 cm H2O for 5-10 seconds. If a spontaneous leak is apparent immediately after dural closure, no Valsalva maneuver will be performed.

Subjects who have a CSF leak will be stratified by surgical procedure, posterior fossa or supratentorial approach, and then randomized to either EVICEL® or DuraSeal™ in a 1:1 allocation ratio.

EVICEL® and DuraSeal™ will be available in the OR/theatre for administration prior to randomization for each subject.

The following activities/assessments will be done during the surgical procedure:

- Review of inclusion and exclusion criteria to confirm intra-operative eligibility. If the subject is no longer eligible, the reason for screen failure will be documented in the source documentation, the screening log, and the eCRF.
- Documentation of concomitant medications as outlined in Section 6.4
- Hospital admission date (for overall Length of Stay)
- Operating room/theatre details:
  - Enter and exit time
  - Procedure time (first incision to final closure)
- Surgical approach – posterior fossa or supratentorial

- Indication for procedure, (e.g. – A-V malformation, Chiari malformation, aneurysm, epilepsy, tumor, other)
  - If tumor, tumor type details (e.g. acoustic neuroma, frontal, meningioma, parietal, temporal, other)
- Tissue patch details (e.g. autologous/non-autologous), if applicable
- CSF leakage determination (prior to randomization)
- Randomization and treatment details (see below)
  - EVICEL® Treatment (to be captured for each layer applied)
    - Method of application (spray or drip)
    - Accessory tips used (if applicable)
    - Number of layers applied
    - Total volume applied
    - EVICEL® units used
  - DuraSeal™ Treatment
    - Number of layers applied
    - Total volume applied
    - DuraSeal™ units used
- Post-treatment Valsalva maneuver details
  - CSF leakage details (if applicable) – breakthrough CSF leakage, delamination, other
- Rescue treatment (if applicable)
- Adverse events from time of application (through follow-up)

#### **7.1.3.1 Subjects Randomized to EVICEL®**

For subjects randomized to receive EVICEL® Fibrin Sealant (Human), a thin layer will be applied to cover the entire length of the suture line and the adjacent, including all suture holes. If necessary, a second layer of EVICEL® may be applied. A cure time of 1-2 minutes should be allotted between layers to allow for clot formation and stabilization. CSF leakage will be evaluated with the Valsalva maneuver performed to an intra-thoracic pressure between 20-25 cm H2O for 5-10 sec.

If a CSF leakage is still apparent a second treatment (up to two layers) with EVICEL® may be applied. CSF leakage will be re-evaluated with the Valsalva maneuver as described above. If watertight closure is achieved for EVICEL® treatment, no further treatment, including the use of onlays, will be allowed.

If watertight closure is not evident after the final Valsalva maneuver, the subject will be deemed a failure and surgeon may revert to his/her standard of care for closure, this can include additional treatment with EVICEL® if clinically appropriate. The use of other fibrin sealants is not permitted.

Subjects randomized to EVICEL® may not have their dura treated with DuraSeal™ Dural Sealant System or any other PEG based or fibrin sealants.

Closure of the remaining layers of the surgical site will be performed according to the surgeon's standard practice.

#### **7.1.3.2 Subjects Randomized to DuraSeal™**

For subjects randomized to DuraSeal™, the assigned product will be applied to the entire length of the suture line, including all suture holes, according to the manufacturer's instruction for use. CSF leakage will

be evaluated with the Valsalva maneuver performed to an intra-thoracic pressure between 20-25 cm H2O for 5-10 seconds.

If a CSF leakage is still apparent, continue treatment with Duraseal™ per manufactures directions. CSF leakage will be re-evaluated with the Valsalva maneuver as described above. If watertight closure is achieved for DuraSeal™ treatment, no further treatment, including the use of onlays, will be allowed.

If watertight closure is not evident after the final Valsalva maneuver, the subject will be deemed a failure and surgeon may revert to his/her standard of care for closure, this can include additional treatment with DuraSeal™, if clinically appropriate. The use of fibrin sealants is not permitted.

Subjects randomized to DuraSeal™ may not have their dura treated with EVICEL® Fibrin Sealant or any other PEG based or fibrin sealants.

Closure of the remaining layers of the surgical site will be performed according to the surgeon's standard practice.

#### **7.1.4 Post-Surgery through Hospital Discharge**

Concomitant medications and adverse events will be collected throughout the study. The following additional information will also be collected post-surgery through discharge:

- ICU time in days
- Laboratory evaluations – collected within 72 hours prior to discharge (labs taken closest to discharge should be used).
  - Electrolyte, blood urea nitrogen (BUN), creatinine
  - Complete blood count (CBC) with differential
  - Liver function tests
- Physical examination (prior to discharge)
  - Surgical site assessment
  - Wound healing assessment
- Hospital discharge date (for overall Length of Stay)

#### **7.1.5 30-Day Follow-up (-/+7 days)**

The following information will be collected at the clinical follow-up approximately 30 days following surgery:

- Adverse events
- Changes in concomitant medications
- Laboratory evaluations
  - Electrolyte, blood urea nitrogen (BUN), creatinine
  - Complete blood count (CBC) with differential
  - Liver function tests
- Physical examination
  - Surgical site assessment
  - Wound healing assessment

#### **7.1.6 60-Day Follow-up (-/+14 days)**

The 60-Day follow-up visit may take place in-person or over the phone. The following information will be collected at the clinical follow-up approximately 60 days following surgery:

- Adverse events, including occurrence of CSF Leak
- Changes in concomitant medications

## **7.2 Procedures for Handling Biological Samples**

### **7.2.1 Laboratory Tests**

All laboratory investigations will be performed at the local hospital laboratory. The volume of blood to be taken will be determined according to the standard practices of each hospital. The normal reference ranges must be provided to Sponsor. Laboratory accreditation certificates must be verified.

## **7.3 Premature Withdrawal of Subjects from the Study**

All randomized subjects should be encouraged to remain in the study until they have completed all follow-up visits. Subjects may discontinue participation in the study at any time and for any reason. However, if the subject decides to discontinue participation in the study, the reason must be documented when possible. Reasons for early withdrawal include, but are not limited to:

- Death;
- Consent withdrawn by the subject;
- Subject refusal to complete study visits and/or procedures;
- Withdrawals due to adverse events
- Lost to follow-up: a certified letter, unless restricted by per local requirements, will be sent to the subject at their last known address, after a minimum of three attempts to reach the subject by telephone have failed. If communication via certified letter is unsuccessful, the subject will be considered lost to follow-up.

Subjects who discontinue from the study prematurely will not be replaced.

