**STATISTICAL DESIGN:**

This is a non-inferiority trial using a one-sided alpha 0.025 and 90% power. The assumed success rate in the both arms is 95%.

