## **3. Overview of Study Design**

This is a single-blinded randomized, controlled study evaluating EVICEL® as an adjunct to sutured dural closure compared to DuraSeal™ Dural Sealant System.

Approximately 230 subjects undergoing posterior fossa or supratentorial procedures (craniectomy or craniotomy) will be enrolled in the trial with at least 60 subjects undergoing posterior fossa procedures being randomized.

Upon completion of the sutured dural repair, the closure will be evaluated for intraoperative cerebrospinal fluid (CSF) leakage with a baseline Valsalva maneuver performed to an intra-thoracic pressure between 20-25 cm H2O for 5-10 sec. If a spontaneous leak is apparent immediately after dural closure, no Valsalva will be performed.

Subjects who have a CSF leak will be stratified by surgical procedure, posterior fossa or supratentorial approach and then randomized to either EVICEL Fibrin Sealant or DuraSeal™ Dural Sealant System in a 1:1 allocation ratio.

Subjects will be followed post-operatively through discharge and again at 30 (-/+7) days and 60 (-/+14) days post-surgery. For the primary endpoint, the incidence of CSF leaks will be assessed up to the 30 day post-operative follow-up period. The incidence of CSF Leak will also be assessed up to the 60 day post-operative follow-up period. A CSF leak will be reported as detected by any of the following: clinical observation, diagnostic testing, imaging or the need for surgical intervention to directly treat a CSF leak.

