5. ANALYSIS SETS

The following three analysis sets defined:

- Intent-to-treat (ITT) set consists of all enrolled and randomized subjects.
- Per-Protocol (PP) set consists of all ITT subjects who have data available for primary effectiveness endpoint and have no major protocol deviations.
- Safety set consists of all enrolled subjects who receive a study treatment.

The primary endpoint will be analyzed using the ITT and the PP set. However, the primary analysis will be based on the PP set. The ITT analysis will be considered confirmatory.

Major protocol deviations are deviations that have an impact on the primary endpoint, or that have an impact on the randomization assignment. These will be determined prior to database lock.

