8.2 Primary effectiveness analysis

The primary endpoint is the proportion of subjects that do not have CSF leak during surgery and up to the 30-day (± 7) post-operative period. A subject is declared success when the following conditions are met:

- Absence of intra-operative CSF leak following Valsalva maneuver, and
- Absence of CSF leak or pseudomeningocele in surgical area during the 30-day follow-up period.

The primary effectiveness parameter will be analyzed using the ITT and Per-Protocol analysis sets. The Per-Protocol analysis will be the primary effectiveness analysis.

The analysis for the ITT set will be performed considering missing data as failures; in addition, sensitivity analyses for the ITT set will be performed considering missing data as successes, and, as worst-case, with missing data for the EVICEL[®] group considered as failures and missing data for the DuraSeal[™] group considered as successes.

The statistical hypothesis for testing the treatment difference is presented as follows:

- $H_0: \Delta \leq -0.10$ tested against the alternative hypothesis
- $H_a: \Delta > -0.10$.

where:

- Δ is the difference between the success rates of Experimental and Control (Experimental minus Control)
- -0.10 is the non-inferiority difference
- The assumed proportion of successes for Control is 0.95.

P_C is the proportion of success in DuraSeal[™] Control subjects and P_E is the proportion of success in EVICEL[®] subjects.

Two hundred and two (202) evaluable subjects (101 per arm) will achieve 90% power to detect a non-inferiority margin difference in group proportions of -0.10. The proportion of successes in the Control group is 0.95. The proportion of successes in EVICEL[®] group is assumed to be 0.85 under the null hypothesis of inferiority. The power was computed for the case when the actual proportion of successes in the EVICEL[®] group is 0.95. The one-sided significance level of the test is 0.025.

If the lower limit of the one-sided 97.5% confidence interval for Δ is greater than -0.10, then it will be concluded that EVICEL[®] is considered to be non-inferior to DuraSeal[™].

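### A subject with no recorded leak who leaves for a complication before Day 30 drops out of the deciding per-protocol analysis, because adverse events and declined visits are allowed to end follow-up

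*Protocol*

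**What the plan says.** Protocol 7.3 asks that randomized subjects be encouraged to complete all visits. It then gives a list headed "Reasons for early withdrawal include, but are not limited to", which places death, refusal of visits or procedures, and "Withdrawals due to adverse events" beside withdrawn consent and loss to follow-up. It asks for the reason to be documented and says these subjects are not replaced. It does not say how their endpoint is scored, or whether leak status is still sought after they leave.

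SAP section 5 states: "Per-Protocol (PP) set consists of all ITT subjects who have data available for primary effectiveness endpoint and have no major protocol deviations". It makes PP the primary analysis and ITT confirmatory. The evaluable set in Protocol 8.2.1 excludes only major violations and has no condition on available data.

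SAP 8.2 and 8.5.1 give three rules for missing data in the ITT set, numbered in SAP Table 14.2.1.2:
- Analysis #1 scores missing as failure in both arms.
- Analysis #2 is the run in which "sensitivity analyses for the ITT set will be performed considering missing data as successes".
- Analysis #3, the worst case, scores missing EVICEL subjects as failures and missing DuraSeal subjects as successes.

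None of these rules separates complication-related exits from administrative ones.

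**The concern.** Protocol 7.1.3 describes treatment that is applied and tested within one operation. After closure there is no study treatment to discontinue, so an adverse event is not in itself a reason to stop observing the subject. Listing it as a reason for leaving, with no provision for further follow-up, turns an outcome that could be observed into a missing one.

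Exits caused by complications are also the exits least likely to be unrelated to the seal. If they are more frequent on EVICEL, leaving them out of the PP set favours the non-inferiority claim. The plan expects some loss: the sample size section enrols about 230 subjects to obtain 202 evaluable, an allowance of 28, or 28/230 = 12.2%.

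**Working it through.** **Inputs from the documents.** The Protocol synopsis states "This is a non-inferiority trial using a one-sided alpha 0.025 and 90% power" and "The assumed success rate in the both arms is 95"%. The margin in SAP 8.2 is -"0.10 is the non-inferiority difference", taken as EVICEL minus DuraSeal. Randomization is "in a 1:1 allocation ratio". The evaluable size is 101 per arm. The documents do not name the confidence-interval method, so the simple Wald limit is assumed.

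**The plan's own figure.** With unpooled variance, n per arm = (1.960 + 1.282)² × (2 × 0.95 × 0.05) / 0.10² = 99.8, so 100 per arm. At 101 per arm the standard error is √(0.095/101) = 0.0307 and the power is Φ(0.10/0.0307 - 1.960) = 0.903. The stated 202 subjects and 90% power are reproduced.

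**Who is affected.**
- A leak after the final Valsalva maneuver is already a failure (Protocol 7.1.3.1 and 7.1.3.2).
- A leak or pseudomeningocele found before exit already fails the success definition (SAP section 3).
- A subject with neither, who leaves before the Day-30 assessment, has no endpoint data. Under SAP section 5 that subject is outside the PP set.

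**Size, illustration 1 (exit counts assumed).** Take 96/101 successes per arm in the PP set, then add k EVICEL-only exits as failures:

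L = 96/(101+k) - 96/101 - 1.96 × √[p_E(1-p_E)/(101+k) + p_C(1-p_C)/101]

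| k | EVICEL success | Difference | Lower limit |
|---|---|---|---|
| 0 | 0.9505 | 0.0000 | -0.0598 |
| 1 | 0.9412 | -0.0093 | -0.0716 |
| 2 | 0.9320 | -0.0185 | -0.0829 |
| 3 | 0.9231 | -0.0274 | -0.0938 |
| 4 | 0.9143 | -0.0362 | -0.1044 |

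For k = 4 the standard error is 0.0348, so L = -0.0362 - 1.96 × 0.0348 = -0.1044. The margin is crossed at the fourth exit.

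**Size, illustration 2 (115 randomized per arm, about 95% success among those assessed, every exit leak-free when last seen; exit counts assumed).**

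| Exits EVICEL / DuraSeal | PP | ITT #1 | ITT #2 | ITT #3 |
|---|---|---|---|---|
| 3 / 0 | -0.060 | -0.090 | -0.057 | -0.090 |
| 4 / 0 | -0.060 | -0.1004 | -0.057 | -0.1004 |
| 8 / 2 | -0.051 | -0.118 | -0.046 | -0.132 |
| 5 / 5 | -0.060 | -0.076 | -0.057 | -0.111 |
| 14 / 14 | -0.060 | -0.096 | -0.053 | -0.199 |

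With 4 against 0, PP and Analysis #2 barely move while Analysis #1 fails. With balanced exits, PP and Analysis #1 both stay inside the margin, even if the whole allowance of 28 is used. Analysis #3 fails in the balanced cases because it is built as a worst case.

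**The case against.** Much of the opposing case stands.

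- **The ITT runs already test this.** Scoring EVICEL exits as failures is ITT Analysis #1, and for EVICEL subjects also Analysis #3. In-text Table T3 shows PP and ITT results together, so an imbalance would be visible. What remains is that the deciding analysis is PP, and the SAP does not say what follows if PP passes and ITT does not.
- **Section 7.3 is a list of reasons, not a scoring rule.** The exclusion arises from the SAP's PP definition combined with the absence of a follow-up provision. The protocol's evaluable set has no data-available condition, so the two definitions also need reconciling.
- **The harmful cases are one-sided.** They assume more exits on EVICEL, and the documents give no expected numbers. The earlier randomized EVICEL study summarised in the Protocol introduction reports similar adverse-event incidence and no deaths. Its control was additional sutures, so it says nothing direct about DuraSeal.

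A reader might infer that the plan inflates the false-positive rate. With true success of 85% against 95%, exact enumeration of the Wald rule at 101 per arm passes 3.3% of the time. If 1, 2 or 3 points of the EVICEL failures are exits that leave the PP set, it passes 5.2%, 8.0% or 12.0%. Those are errors only if an exit is first defined as a failure, and the plan's endpoint is leak or pseudomeningocele. Among assessed subjects the EVICEL rates are 0.85/0.99, 0.85/0.98 and 0.85/0.97, or 85.9%, 86.7% and 87.6%. The differences from 95% are -9.1, -8.3 and -7.4 points, all inside the margin. With 2 points of exits in both arms the pass rate is 3.6%.

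**Conclusion.** The point holds in a limited form. The plan lets an adverse event or a declined visit end observation after a one-time treatment, and the SAP then removes subjects with no recorded leak and no Day-30 status from the analysis that decides non-inferiority. Under the assumed event counts and a Wald limit, an excess of four EVICEL exits separates a PP limit near -6 points from a limit beyond -10 when those exits are scored as failures. Balanced exits have little effect on the conclusion.

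A reader might go further and say that patients lost to complications in general become missing and are credited as sealing successes. The documents do not support that. Earlier leaks and pseudomeningoceles are already failures, only Analysis #2 credits success in both arms, and Analysis #1 scores every such exit as a failure. Nor do the documents suggest that exits will be more frequent on EVICEL. This is a cheap improvement to the primary data, not a flaw that invalidates the design.

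**What to change.** 1. In Protocol 7.3, keep the withdrawal reasons, because they document why subjects left. Deleting the adverse-event reason would only hide it.
2. Add there that an adverse event, or a declined visit or procedure, does not end follow-up. Leak and pseudomeningocele status to Day 30 is then obtained from medical records or by phone unless consent to data collection is withdrawn. Protocol 7.1.6 already accepts phone contact at 60 days. These subjects then stay in the PP set with observed outcomes.
3. Report deaths and adverse-event exits before Day 30 by arm beside the primary result. SAP Listing 16.2.1.1 already holds the reason for and time to withdrawal.
4. Leave Analysis #3 unchanged for DuraSeal subjects. Scoring their deaths as failures would make the worst case easier for EVICEL to pass: if all exits in the 5 / 5 example were deaths, its limit would move from -0.111 to -0.076.
5. Reconcile the PP definitions in Protocol 8.2.1 and SAP section 5.

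The cost is a few sentences, a small table and a little extra site work. Phone contact may miss a pseudomeningocele that is seen only on examination, so the source of each outcome should be recorded.
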